## Transcutaneous Electrical Nerve Stimulation (TENS) for Pain Alleviation in Perioperative Fracture Patients

### Specific Aims:

Opioid overdoses continue to increase, and the path to addiction often begins with a prescription. Half of postoperative patients receive an opioid prescription. Multimodal pain management, including cognitive, physical, and pharmaceutical strategies, reduces reliance on opioids alone. Transcutaneous nerve stimulation (TENS) is one physical strategy; this study aims to evaluate the effectiveness of TENS as part of postoperative pain management.

**Specific Aim 1:** To pilot the use of TENS among a postoperative lower extremity injury population as part of multimodal pain management.

$H_0$ : TENS cannot be delivered safely among this population.

$H_A$ : TENS can be delivered safely among this population.

**Specific Aim 2:** To compare utilization of inpatient and outpatient pain medications of patients treated with TENS and historical controls.

$H_0$ : Patients treated with TENS will require the same amount of opioids as historical controls.

$H_A$ : Patients treated with TENS will require less opioids (lower morphine milligram equivalent – MME) than historical controls during hospitalization and throughout 3-month follow up.

**Specific Aim 3:** To compare patient-reported outcomes of patients treated with TENS and historical controls.

$H_0$  1: Patients treated with TENS will experience equivalent patient-reported outcomes as compared to historical controls.

$H_A$  1: Patients treated with TENS will experience greater improvement in patient-reported outcomes (PROMIS 29) relative to baseline as compared to historical controls.

$H_0$  2: Patients treated with TENS will report higher pain scores as compared to historical controls.

$H_A$  2: Patients treated with TENS will report equivalent or lower pain scores as compared to historical controls.

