#### Sample Size:

The sample size estimate was based on data from the meta-analysis conducted by Tedesco et al. This is a superiority prospective observational study with matched historical controls and the primary outcome variable is morphine milligram equivalents (MME) within the first 48 hours postoperatively. The assumed mean MME for the TENS group is 6.4 and 9.9 for the control group with a pooled standard deviation of 5.5. Using a two-sided independent T-test, .05 level of significance and 80% power, 40 patients per group is needed for a total study sample of 80 patients. Therefore, we will enroll 50 patients in order to account for loss to follow-up. Historical controls will be injury-matched from a prospectively collected, historical database on mobility (N=50).

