#### Outcome Measures:

**Primary Outcomes:** The primary outcome will be inpatient and outpatient opioid use, defined as morphine milligram equivalents. Morphine milligram equivalent dose (MME) will be calculated to standardize across different medications. Pill counts will be conducted at follow-up visits to account for unused opioids, and patients will be provided with opioid disposal kits. Use of non-opioid pain medications (i.e. NSAIDS, acetaminophen, gabapentin) will be documented. Patients will also be asked about their use of nonpharmaceutical modalities at each follow-up visit or phone call, including cryotherapy, aromatherapy, and cognitive strategies.

**Secondary Outcomes:** The secondary outcomes will be patient-reported outcomes, measured by the PROMIS 29, which includes physical function, anxiety, depression, fatigue, sleep disturbance, ability to participate in social roles and activities, pain interference and pain intensity. In addition, pain scores from the inpatient stay and clinic visits will be abstracted from the medical record. PROMIS will be administered during the hospitalization and at follow-up visits or via phone calls, emails, or text messages at 2, 6, and 12 weeks. VAS pain scores will be abstracted from the medical record during the hospitalization and at each follow-up visit.

**Process Measures and Feasibility:** Process measures will be collected to document feasibility of implementing TENS postoperatively among this patient population, including: patient compliance with TENS after discharge, number of times each day TENS was used, duration of each TENS session, and average frequency/amplitude of electrical current for each patient.

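### Aim 3 hypothesis 2 claims equivalent or lower pain without a margin, so read literally it can show only lower pain, and a non-significant result could be misread as equivalence

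*Protocol*

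**What the plan says.** Aim 3 in the Protocol's Specific Aims has two hypothesis pairs. The second concerns pain:

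- Null: "Patients treated with TENS will report higher pain scores as compared to historical controls".
- Alternative: "Patients treated with TENS will report equivalent or lower pain scores as compared to historical controls".

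The first pair concerns PROMIS 29 and uses the same word on the other side. There the null is that "Patients treated with TENS will experience equivalent patient-reported outcomes as compared to historical controls", and the alternative is greater improvement with TENS.

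Under Outcome Measures, pain is a secondary outcome: "VAS pain scores will be abstracted from the medical record during the hospitalization and at each follow-up visit". Neither that section nor any other gives a margin, an equivalence range or an SD for pain.

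The Sample Size section calls the study one of superiority ("This is a superiority prospective observational study with matched historical controls") and sizes it on MME in the first 48 hours: "Using a two-sided independent T-test, .05 level of significance and 80% power, 40 patients per group is needed". It plans 50 TENS patients and 50 controls. No test or power statement is given for pain.

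**The concern.** Putting worse in the null and not worse in the alternative is the usual direction for a non-inferiority claim. Such a claim needs a margin: the null should be that pain is higher by at least some stated amount. Here the null is simply that pain is higher, so equality sits on the edge of the alternative, where no valid test can have power above its alpha.

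This matters because lower opioid use with unchanged pain is a realistic result; the Background itself cites studies that found no difference in pain scores. The conclusion wanted alongside lower MME would be that pain was not worse. As written, the pair would hardly ever deliver it when pain is truly equal. The practical risk is the shortcut: a two-sided test is run, it is not significant, and the result is reported as equivalent pain.

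**Working it through.** **Inputs.** From the Sample Size section: 40 per group required, 50 per group planned, two-sided 0.05, 80% power, MME means 6.4 and 9.9, SD 5.5. The protocol gives no SD and no margin for pain, so pain differences are in SD units and the margins below are assumptions, shown as a range. The model is an unadjusted comparison of two independent groups of equal size and equal SD.

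**1. The plan's own figure.** The standardised MME difference is (9.9 − 6.4)/5.5 = 3.5/5.5 = 0.636. The two-sided t-test solution for 80% power is 39.75, rounded up to 40 per group, with power 0.803 at 40. The stated figure reproduces and is not in dispute. It concerns MME only.

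**2. The pair read literally.** Let d be mean pain on TENS minus mean pain in controls. The null is d > 0 and the alternative d ≤ 0. A valid test must reject with probability at most alpha for every d > 0. Power is continuous in d, so it is also at most alpha at d = 0. In the normal approximation, with benefit b = −d in SD units,

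P(support alternative) = Φ(b/√(2/n) − z(1−α)).

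| True benefit b | n = 40, one-sided 0.025 | n = 50, one-sided 0.025 |
|---|---|---|
| 0 (equal pain) | 2.5% | 2.5% |
| 0.2 SD | 14% | 17% |
| 0.5 SD | 61% | 70% |

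At one-sided 0.05 the first row is 5%. That row does not depend on n. The test behaves as an ordinary one-sided test for lower pain.

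**3. What a non-significant two-sided test leaves open.** The 95% CI half-width is t(0.975, 2n−2) × √(2/n):

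- n = 40: √(2/40) = 0.2236; half-width 0.445 SD.
- n = 50: √(2/50) = 0.2000; half-width 0.397 SD.

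With an observed difference of exactly zero, an increase of up to about 0.45 or 0.40 SD is still inside the interval. At the edge of non-significance the observed increase is itself one half-width, so the upper limit approaches 2 × 0.445 = 0.89 SD or 2 × 0.397 = 0.79 SD.

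**4. What a margin would need.** With margin m, true equality, one-sided 0.025 and a noncentral t with noncentrality m√(n/2):

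| Assumed margin | Power, n = 40 | Power, n = 50 | n per group for 80% |
|---|---|---|---|
| 0.3 SD | 26% | 32% | 176 |
| 0.5 SD | 60% | 70% | 64 |

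The smallest margin with 80% power is 0.634 SD at 40 and 0.566 SD at 50 per group. The normal approximation (1.960 + 0.842) × √(2/n) gives 2.802 × 0.2236 = 0.63 and 2.802 × 0.2000 = 0.56, in close agreement.

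**The case against.** The strongest reply is that a margin, a test and a decision rule for a secondary outcome are commonly left to the SAP, which is not at hand. Moreover, equivalent may mean not meaningfully higher. Aim 2 speaks of the same amount of opioids while Aim 3 says equivalent, so the choice of word may be deliberate. On that reading the alternative already includes differences below some margin, and an SAP could supply it without contradicting the text. This stands in part: the zero boundary is the literal reading, not the only one. Against it, the first Aim 3 pair uses the same word for an ordinary null of no difference, and a null of simply higher pain does not exempt small increases. The protocol states the pair itself and leaves its key word undefined, so the wording is a fault of this document and not only a detail left open.

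Other parts of the reply also stand. The 2.5% to 5% holds for any test with its boundary at zero and is not special to this trial. The SD margins are assumptions. A repeated-measures or baseline-adjusted analysis of the several VAS scores could be more precise than the simple comparison used here.

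Three stronger readings are tempting, but the protocol does not support them:

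- *That the superiority label contradicts this pair.* The label and the two-sided test are stated with MME as the primary outcome, and a no-worse secondary hypothesis beside a superiority primary is not a contradiction in itself.
- *That it is unclear which pain measure is meant, because PROMIS 29 also covers* "ability to participate in social roles and activities, pain interference and pain intensity". Aim 3 ties its first pair to PROMIS 29, and Outcome Measures brings in pain scores separately ("In addition, pain scores from the inpatient stay and clinic visits will be abstracted from the medical record") and then calls them VAS.
- *That the sponsor must turn the pain question into a superiority test.* That is a choice for the sponsor; a justified margin is an equally sound answer.

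**Conclusion.** The concern holds in limited form. Read literally, Aim 3 hypothesis 2 has its boundary at zero, so when pain is truly equal the alternative is supported only 2.5% to 5% of the time and the equivalent part cannot be established. If the MME test were reused for pain, which the protocol does not say, a non-significant result would be compatible with a considerable increase in pain: the 95% CI half-width is about 0.45 SD at 40 and 0.40 SD at 50 per group. The first result needs no assumption about the SD or a margin; the second rests on a simple two-sample comparison with equal SDs.

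A reader might infer that the trial's main conclusion is at risk. It is not: pain is secondary, and the primary MME comparison and its 40 per group are untouched. The wording should be corrected, but the matter is modest.

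**What to change.** Reword hypothesis 2 of Aim 3 in one of two ways.

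- **(a) Keep the no-worse claim.** State the null as abstracted VAS pain higher with TENS by at least a pre-specified, justified margin. Judge the alternative by whether the upper limit of the two-sided 95% CI for the difference lies below that margin.
- **(b) If no margin can be justified.** Delete the equivalence wording, state the alternative as lower pain with the null as its complement, and report the difference with its 95% CI.

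In both cases add a sentence that a non-significant difference will not be described as equivalence.

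Cost: either route changes one hypothesis pair and needs no new data. Under (a) the margin needs a clinical justification, and at the planned size only a wide one (about 0.63 SD at 40 or 0.57 SD at 50 per group) has 80% power under true equality. Under (b) the formal no-worse claim is given up and the interval carries most of the information.

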### Background and Significance:

Transcutaneous electrical nerve stimulation (TENS) is an affordable and non-invasive option for post-operative analgesia. Broadly, TENS devices deliver pulsed electrical impulses across skin to modulate pain. They are theorized to work through different mechanisms at multiple physiologic levels. Centrally, TENS units activate small-diameter sensory afferents (A $\delta$  nerve fibers), which in turn activate descending pain-inhibitory networks. Peripherally, TENS activation of both large- and small-diameter sensory afferents blocks nociceptive signals to the

brain and is instead perceived as TENS-induced paresthesias. Finally, TENS efficacy may also be mediated by  $\mu$ -opioid, 5HT-1, and 5HT-2 receptors, particularly at low-frequency electrical activity.

There are inconclusive results for the adjunctive use of TENS to modulate pain, largely because of a relative paucity of high-quality trials and significant inter-study heterogeneity due to non-standardized protocols. Moreover, most studies within the orthopaedic literature have been concentrated primarily within the total knee arthroplasty (TKA) literature and may have limited generalizability to orthopaedic trauma patients. Some studies have shown a trend towards decreased opioid consumption with the adjunctive use of TENS (vs. placebo-TENS or standard care) while other studies have shown no difference in pain scores in the post-operative period. To our knowledge, only two recent RCTs have been conducted on non-TKA orthopaedic populations, both of which show promise for the use of TENS postoperatively. One prospective double-blind randomized trial on arthroscopic rotator cuff repairs found a 25% reduction in post-operative opioid consumption when TENS was used adjunctively for pain control. Another single-blind prospective RCT on Colles' fractures reported greater postoperative pain improvements in patients receiving TENS vs. placebo.

There is a growing body of evidence to suggest that TENS therapy can reduce post-operative pain after orthopedic procedures. More high-quality studies are needed to strengthen this suggestion and to characterize specific protocols, populations, and orthopedic conditions for which it might work best. Transcutaneous electrical nerve stimulation, if shown to be effective, stands to serve as an affordable non-opioid, non-invasive option for the safe and effective treatment of pain in the orthopaedic trauma patient population.

TENS units are a non-significant risk device and, therefore, do not require an IDE based upon FDA guidance. The sensor pads will be placed at the same time as the surgical fixation of the study injury. It does not present a potential serious risk to the health and welfare of patients.

## **Research Design and Method:**

### Overall Design

This will be a prospective observational study of patients undergoing operative treatment of lower extremity conditions, including fracture fixation, treatment of nonunion, and deformity correction. The study will be conducted at a single Level I trauma center. Enrolled patients will receive TENS postoperatively during hospitalization; TENS units will also be sent home with patients for use throughout recovery. This group will be compared to controls injury-matched from a prospectively collected, historical database on mobility who did not receive treatment with TENS.

### Inclusion Criteria:

- Operative treatment of lower extremity conditions, including fracture fixation, treatment of nonunion, and deformity correction
- Injury or deformity of the femur, tibia (plateau, shaft, pilon), or hindfoot and ankle
- Isolated injury
- 18 years or older
- Able to provide consent

- Plan for discharge to home

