#### Exclusion Criteria:

- under 18 years of age
- Unable to provide consent (no use of LAR)
- History of dementia or Alzheimer's disease
- Patient residing in a residential care facility prior to admission (i.e, skilled nursing facility, nursing home, assisted living facility)

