#### Treatment Groups:

The prospectively enrolled patients will have TENS pads placed immediately following surgery, prior to PACU. The TENS unit will be connected to the pads and turned on in the PACU. Each patient will receive instructions for suggested use of the device. They will be allowed to individualize the frequency/amplitude of the current to reach a "strong sub-noxious" stimulation, as recommended by previous studies. They will be asked to aim for 4x45 minute sessions each day. This protocol was previously published by a separate group demonstrating decreased post-operative pain levels with adjunctive TENS use.

This institution has an ongoing research study which collects injury characteristics, patient-reported outcomes, and kinematic/performance data for orthopaedic trauma patients with lower-extremity injuries. Patients with similar injuries as the prospectively enrolled patients will be identified in this database to serve as controls, because TENS units were not previously used at this institution for pain management. Our institution also has a database of all opioid prescriptions as well as risk factors that can be used to provide these data for the controls.

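### Historical controls are matched on injury only, so opioid use before surgery, which feeds directly into the MME outcome, is left unbalanced within an injury type

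*Protocol*

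**What the plan says.** Under Inclusion Criteria, the protocol admits "Operative treatment of lower extremity conditions, including fracture fixation, treatment of nonunion, and deformity correction". The other inclusion criteria concern anatomical site, isolated injury, age, consent and planned discharge home. The exclusions are age, inability to consent, dementia, and "Patient residing in a residential care facility prior to admission". Neither list refers to opioid use before the operation.

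The Overall Design and Sample Size sections describe the controls as injury-matched from a historical mobility database, and Treatment Groups speaks of patients with similar injuries. No other matching factor is named.

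For sizing, "the primary outcome variable is morphine milligram equivalents (MME) within the first 48 hours postoperatively". The Outcome Measures section defines the primary outcome more widely, as inpatient and outpatient opioid use, again in MME.

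Two sources could bear on prior use. Treatment Groups says: "Our institution also has a database of all opioid prescriptions as well as risk factors that can be used to provide these data for the" (the sentence closes by naming the control group). For TENS patients, the Baseline paragraph of Study Procedures abstracts drug and non-drug pain management from the medical record. Neither source is linked to how controls are chosen, and neither passage names opioid use before surgery.

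**The concern.** MME counts every opioid taken in the window. A patient who arrives on daily opioids brings that dose into the outcome regardless of what TENS does. This follows from how the outcome is defined and needs no outside evidence.

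In a randomised trial, chance would balance prior use on average. Here only the matching rule can balance it at the design stage, and the rule stops at injury. Matching on injury should help to pair a nonunion with a nonunion and an acute ankle fracture with another, provided the database holds such cases. It does not make two patients with the same injury alike in prior opioid use. If the shares of prior users differ between the groups, part of the MME difference reflects who was selected. The planned difference is only 3.5 MME, so modest excesses per patient count.

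**Working it through.** **Inputs from the protocol (Sample Size).** "The assumed mean MME for the TENS group is 6.4 and 9.9 for the control group", "with a pooled standard deviation of 5.5". The planned difference is 9.9 − 6.4 = 3.5 MME. "Using a two-sided independent T-test, .05 level of significance and 80% power, 40 patients per group is needed".

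**The plan's own figure.** For a two-sided, two-sample t-test with standardised difference 3.5 / 5.5 = 0.636, the exact calculation gives 39.7 per group, so 40. Power at 40 per group is 80.3%. The stated size reproduces and is not in question.

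**Inputs that are assumed.** The documents give neither the extra 48-hour MME per prior user (D) nor the imbalance in the share of prior users (Δp). I take D as half to one times the planned control mean, that is 4.95 to 9.9 MME over 48 hours, or about 2.5 to 5 MME per day. I take Δp as 10 or 20 percentage points, which is 4 or 8 patients of 40.

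**Formula.** Bias in the mean difference = Δp × D. The last two columns use the noncentral t with 40 per group and SD 5.5, with no adjustment for prior use. The false-positive rate supposes that TENS has no effect. The power column supposes a true difference of 3.5 and prior users more common in the TENS group, so that the expected difference is 3.5 − bias.

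| Δp | D | Bias (MME) | Share of 3.5 | False-positive rate (nominal 5%) | Power (planned 80%) |
|---|---|---|---|---|---|
| 0.10 | 4.95 | 0.50 | 14% | 6.8% | 67% |
| 0.10 | 9.9 | 0.99 | 28% | 12.5% | 52% |
| 0.20 | 4.95 | 0.99 | 28% | 12.5% | 52% |
| 0.20 | 9.9 | 1.98 | 57% | 36% | 23% |

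**Break-even.** With a 10-point imbalance, half the planned effect (1.75 MME) needs D = 1.75 / 0.10 = 17.5 MME over 48 hours. The whole effect needs D = 3.5 / 0.10 = 35. Both lie above the range assumed here.

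**The case against.** The strongest reply has four parts.

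*The data route exists.* A reader might infer that the prescription database serves only to supply control outcomes. The text does not support that: it offers risk factors as well as prescriptions, and baseline pain-medication use is abstracted for TENS patients. This part stands. What remains is that neither source is tied to control selection and that no common definition of prior use is set for the two groups.

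*The SAP may adjust.* It may, and the SAP is not shown. The t-test is named only as the basis for the sample size, so the documents do not establish that the analysis will be unadjusted. The matching rule, however, is fixed in the protocol. Adjustment would also need prior use to be recorded comparably in both groups, which the protocol does not secure.

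*Broad eligibility is defensible.* Aim 1 is a pilot, and admitting a range of patients suits it. One might infer that prior users should be excluded. That would trade generalisability for balance and is not needed, because the weakness lies in the matching rule.

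*The size is assumed.* True. It is tempting to say that a small imbalance could produce or hide most of the planned effect. On the range used here a 10-point imbalance moves at most 28% of it, and only the 20-point imbalance with the largest excess passes half. Nor can one conclude that the SD of 5.5 is too low. The figures are said to come from a meta-analysis, and the protocol does not say whether its patients included prior users.

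**Conclusion.** The point holds as a weakness of the matching rule. The primary outcome is MME, allocation is not random, injury is the only stated matching factor, and prior opioid use adds directly to the outcome. Followed as written, the plan leaves this factor unbalanced within injury type.

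If a prior user takes 4.95 to 9.9 MME more over 48 hours, the shift is 0.5 to 1.0 MME for a 10-point imbalance (14% to 28% of 3.5; false-positive rate about 7% to 12.5%). It is 1.0 to 2.0 MME for a 20-point imbalance (28% to 57%). These figures rest on the assumed excess and imbalance, on SD 5.5 with 40 per group, and on an unadjusted comparison. The direction is unknown. The documents do not show that an imbalance will occur, only that the stated design does nothing to prevent one. The change is worth making before controls are selected, but the study does not fail without it.

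**What to change.** Keep the eligibility criteria as they are.

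1. Classify every TENS patient and every candidate control in the same way from the institutional prescription database: any opioid prescription, yes or no, over one fixed look-back ending at the index injury, or at surgery for elective cases.
2. Add this status as a matching factor alongside injury in Overall Design, Treatment Groups and Sample Size.
3. Where a TENS patient has no control matched on both, keep the injury match and adjust the primary comparison for prior opioid prescription.

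The work is one query of a database the institution already holds and a sentence in each of three sections. There are two drawbacks. The number of eligible controls falls by an amount that depends on the size of the pool, which the protocol does not give. The mobility database is described as covering orthopaedic trauma, so controls for nonunion and deformity cases may already be few. Some patients may also be misclassified if prescriptions written outside the institution are not captured. Using one source and one look-back for both groups at least applies the same definition to each.

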#### Study Procedures:

**Screening & Enrollment:** All patients 18 years or older presenting for initial treatment, nonunion or limb length deformity correction of the femur, tibia (plateau, shaft, pilon), or hindfoot/ankle will be screened for eligibility. Once eligibility has been confirmed, a research coordinator and/or investigator will approach patient for consent prior to surgery. Patients will be given the opportunity to review the informed consent document and ask questions about the study. The informed consent will comply with the ICH/GCP regulatory guidelines.

**Baseline:** Once consent is obtained, baseline data regarding participant characteristics, injury characteristics and PROMIS scores will be collected from the participant and entered into the electronic data collection system. Data will also be collected from the medical record regarding injury characteristics, fracture fixation, pain scores and utilization of pain alleviation modalities (pharmaceutical and nonpharmaceutical).

**Follow-up:** Participants will complete study visits at 2, 6, and 12 weeks following admission to the hospital, which may overlap with regularly scheduled standard of care clinic visits. These visits may also be completed via phone calls, text messages, or email. At these visits, participants will be asked to complete PROMIS-29 survey. Data regarding use of any pharmaceutical and nonpharmaceutical modalities for pain management will be collected at these visits. Additional variables about fracture complications will be collected from the electronic medical record.

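### Eligibility includes deformity correction, but controls are matched on injury alone from a database described as trauma injuries, so these patients may lack a like-for-like control in Aims 2 and 3

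*Protocol*

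**What the plan says.** **Who is enrolled.** The Inclusion Criteria admit "Operative treatment of lower extremity conditions, including fracture fixation, treatment of nonunion, and deformity correction". The anatomical criterion treats injury and deformity as alternatives: "Injury or deformity of the femur, tibia (plateau, shaft, pilon), or hindfoot and ankle". The same list also requires "Isolated injury" of every patient. Under Study Procedures, screening covers patients "presenting for initial treatment, nonunion or limb length deformity correction of the femur, tibia (plateau, shaft, pilon), or hindfoot/ankle", which names only limb length deformity.

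**Where controls come from.** Overall Design states: "This group will be compared to controls injury-matched from a prospectively collected, historical database on mobility". Treatment Groups describes the source as an ongoing institutional study that collects, among other items, "kinematic/performance data for orthopaedic trauma patients with lower-extremity injuries", and gives the selection rule: "Patients with similar injuries as the prospectively enrolled patients will be identified in this database to serve as controls". The Sample Size section repeats that matching is on injury and sets 50 controls. No other matching factor is named, and no rule says how a deformity or nonunion patient is matched.

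**Size.** The Sample Size section plans 40 per group for 80% power on MME in the first 48 hours. It enrols 50 TENS patients and gives loss to follow-up as the reason for the extra 10.

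**The concern.** Aims 2 and 3 rest wholly on the historical comparison, since there is no concurrent control arm. The comparison is interpretable only for conditions present on both sides. Eligibility is written in terms of conditions (fracture, nonunion, deformity), while the control pool and the matching rule are written in terms of injury alone. For a patient whose indication is a deformity, matching on injury is not defined.

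There are two possible consequences:

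- The patient is paired with the nearest injury by site, most likely an acute fracture. Any difference in opioid need between planned deformity surgery and acute fracture surgery then enters the estimated TENS effect.
- The patient is left out of the matched comparison, which reduces the number analysed.

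The first matters more, because it biases the estimate whatever the attrition.

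**Working it through.** **Step 1. Reproduce the planned size.** Inputs from the Sample Size section: means 6.4 and 9.9, SD 5.5, two-sided alpha 0.05, power 80%.

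- Difference: 9.9 − 6.4 = 3.5. Standardised: 3.5 / 5.5 = 0.636.
- Two-sample t-test (noncentral t): 39.75, so 40 per group, with power 80.3%. The stated figure reproduces.
- Allowance: 40 / (1 − 0.20) = 50. The enrolment figure implies 20% loss. With 50 per group and no loss, power is 88.3%.

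**Step 2. Deformity patients compared with fractures.** Let f be their share of the TENS group and b the difference in mean 48-hour MME between them and the fracture controls that has nothing to do with TENS. The bias in the estimated difference is f × b. The protocol gives neither value, so both are assumed: f = 10-30%, b = 0.5-1 SD (2.75-5.5 MME). The rejection rate is the t-test's power at a standardised shift of f × b / 5.5 when TENS has no effect, with the SD held at 5.5.

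| f | b (MME) | Bias (MME) | Share of 3.5 | Rejection rate, 40 per group | Rejection rate, 50 per group |
|---|---|---|---|---|---|
| 10% | 2.75 | 0.28 | 8% | 5.6% | 5.7% |
| 10% | 5.5 | 0.55 | 16% | 7.3% | 7.9% |
| 20% | 2.75 | 0.55 | 16% | 7.3% | 7.9% |
| 20% | 5.5 | 1.10 | 31% | 14.3% | 16.8% |
| 30% | 2.75 | 0.83 | 24% | 10.2% | 11.5% |
| 30% | 5.5 | 1.65 | 47% | 26.3% | 31.8% |

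The direction is unknown. For f = 20%, b = 5.5 and a true effect of 3.5, the expected difference is 3.5 + 1.1 = 4.6 if deformity patients need less opioid than fractures. It is 3.5 − 1.1 = 2.4 if they need more. At 40 per group the chance of a significant result is then 95.9% or 48.7%, against the planned 80.3%.

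**Step 3. Deformity patients left unmatched.** Power for a difference of 3.5 and SD 5.5, by assumed unmatched share:

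| Scenario | 10% | 20% | 30% |
|---|---|---|---|
| No other loss, all 50 controls kept (45/40/35 TENS) | 86.5% | 84.3% | 81.4% |
| No other loss, the control dropped too (45/40/35 pairs) | 84.7% | 80.3% | 74.7% |
| 20% other TENS loss, all 50 controls kept (36/32/28 TENS) | 82.1% | 79.3% | 75.9% |
| 20% other loss, the control dropped too (36/32/28 pairs) | 75.9% | 70.7% | 64.8% |

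If pairs are dropped, 40 of 50 must remain to keep 80%, so total loss may reach 20%. If all 50 controls are kept, 33 TENS patients still give 80.1%, so total TENS loss may reach 17/50 = 34%.

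**Step 4. Eligibility wording side by side.** The Inclusion Criteria admit injury or deformity, yet also require "Isolated injury", which does not literally fit a deformity without injury. They admit deformity correction generally, while screening names only "nonunion or limb length deformity correction". These statements describe different populations.

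**The case against.** The strongest objection is that the contents of the database are not known. A patient with a post-traumatic deformity or a nonunion is still an orthopaedic trauma patient and could be in it, and the protocol also calls it a database on mobility. With the isolated-injury criterion and a Level I trauma center as the setting, an enrolled deformity patient may well have an index injury that can be matched. This stands. A reader might infer that these patients have no valid match at all, but no sentence in the protocol says so. What remains is that injury and deformity are written as alternatives, and the selection rule speaks only of injuries.

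A reader might also infer that the stated 80% power is lost. That does not follow. The planned test is an independent t-test with 50 controls fixed, so losing a TENS patient need not remove a control, and a 48-hour endpoint should suffer little from loss at the later visits. The lowest figures in Step 3 need dropped pairs on top of a full 20% loss.

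The bias figures rest on an assumed share and an assumed difference, and the largest rejection rate needs both extremes together. That is correct, and they are offered as illustration only.

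Finally, matching details are commonly left to a statistical analysis plan, which is not at hand. That covers the algorithm and the handling of unmatched patients. It does not cover the mismatch between eligibility and control source: both are fixed in the protocol, and no analysis can supply controls of a kind the source does not hold.

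**Conclusion.** The concern holds in a limited form. Eligibility is wider than the control source as described, and the only stated matching factor is undefined for one eligible condition. Following the plan can therefore pair planned deformity surgery with acute fractures and bias Aims 2 and 3. At an assumed 20% share and a 1 SD difference, the shift is 1.1 MME, or 31% of the planned 3.5, with a false-positive rate of about 14% (40 per group) to 17% (50 per group). The direction is unknown, so a real effect could equally be hidden. Loss of power is conditional and secondary: it needs more than about 20% of pairs, or about 34% of TENS patients if all 50 controls stay in. The sample size calculation itself is correct. How serious the problem is depends on one fact the protocol does not give: how many deformity and nonunion cases the database holds.

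**What to change.** 1. Before enrolment, count the control candidates in the database by condition: acute fracture by site, nonunion, deformity correction.
2. State that controls are matched on condition and procedure type as well as anatomical site.
3. Limit the Aim 2 and 3 comparisons, and the 50 matched patients, to conditions the database holds. Any other eligible patients contribute to Aim 1 only, outside the 50. If the count shows enough deformity cases, they stay in the comparison; removing them before the count is not warranted.
4. Reconcile the isolated-injury, injury-or-deformity and deformity-correction wording of the Inclusion Criteria with the limb-length wording under Study Procedures, so that one population is described throughout.

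The cost is a database query and a wording change. The possible downside is a narrower comparative population and slightly slower recruitment.
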